Budget, funding	[name], AUH, Skejby – [contact]
Legal advisor	[name], TTO, Aarhus University - [contact]

1) Dep. Cardiology, Aarhus University Hospital, Skejby. [contact] [contact]
[name]

2) Biomedical Instrument Institute, School of Biomedical Engineering, Shanghai Jiao Tong University, Shanghai, China

3) Division of image processing, Leiden University Medical Centre, Leiden, The Netherlands

4) Medis medical imaging, Leiden, The Netherlands

Abbreviations

AMI	Acute Myocardial Infarction
-----	-----------------------------

AP	Angina Pectoris
AS	Area Stenosis
CABG	Coronary Artery Bypass Grafting
CCS	Canadian Cardiovascular Society Angina Grading System
CK-MB	Creatinine Kinase MB
CRF	Case Report Form
FFR	Fractional Flow Reserve
GCP	Good Clinical Practice
IHD	Ischemic Heart Disease
LBBB	Left bundle branch block
MACE	Cardiac Death, Myocardial Infarction, Stent Thrombosis or Target Vessel Revascularization
MI	Myocardial Infarction
MV	Main Vessel
PCI	Percutaneous Coronary Intervention
QCA	Quantitative Coronary Analysis
QFR	Quantitative Flow Ratio
TNI	Troponin I
TNT	Troponin T
TLR	Target Lesion Revascularization
TVR	Target Vessel Revascularization
TLF	Target Lesion Failure
TVF	Target Vessel Failure

1. Background

Patients in high risk of having one or more coronary stenoses are evaluated routinely by invasive coronary angiography (CAG) and often in combination with measurement of fractional flow reserve (FFR) during the procedure¹. Stenosis identified by angiography is considered to cause ischemia if the narrowing results in a lumen reduction of more than 90% diameter stenosis by visual estimate. If the lumen reduction is between 30% and 90% it is indicated to measure FFR to assess if the flow is reduced more than 20% by the stenosis. Such a reduction in flow is correlated to ischemia in the downstream myocardium^{2,3}. FFR is assessed during CAG by advancing a wire with a pressure transducer towards the stenosis and measuring the ratio in pressure between the two sides of the stenosis during maximum blood flow (hyperemia). Hyperemia is induced by adenosine infusion during the measurement.

This strategy of FFR-guided intervention in coronary artery disease is well established by solid clinical evidence and has gained the highest guideline recommendations in Europe¹. In Denmark FFR is measured in an estimated 4000 patients a year.

Pros and cons of FFR

The solid evidence for FFR evaluation of coronary stenosis and the relative simplicity in performing the measurements have supported wide spread adoption of the technology. However, the need for interrogating the stenosis by a pressure wire carries the risk of dissecting or even perforating the vessel. The wire can also dissect a plaque and cause plaque rupture and thrombus can form around the catheter. These complications are relatively rare but may be detrimental. Another factor is the price where pressure wires and adenosine adds substantially to the procedural costs. Cost-effectiveness analysis has shown that an FFR guided strategy is cost-effective compared to an angiographic guided strategy as fewer stents are implanted per patient⁴. Still, if the cost of doing FFR could be reduced or alleviated it would definitely benefit the economically restrained health care systems.

Wire-free FFR

A new method (QFR by Medis medical imaging) for evaluation of the functional significance of coronary stenosis is based on computer calculation of the FFR value. This calculation is performed by analysing the coronary angiogram and thus reduces or potentially eliminates the need for measuring FFR by pressure wires. The QFR method combines a 3D reconstruction of the target

vessel based on two angiographic projections and the contrast flow velocity to compute the “FFR value”. In the presented FAVOR study, QFR was shown to be very promising and results on in-procedure analysis from the WIFI I trial are imminent. Development of similar methods is ongoing in multiple companies and academic groups⁵⁻⁷ and at present we are not aware that similar methods are tested for in-procedure computation of FFR. The FAVOR study evaluating the QFR technology showed good diagnostic accuracy in comparison to FFR when QFR was based on angiographic views acquired with and without induced hyperaemia.

The available version of the method is capable of assessing QFR during CAG but is not yet CE-marked and has not received FDA approval for clinical decision-making, but it allows evaluation of the feasibility and diagnostic precision of this novel method.

1.1 Purpose

To evaluate the feasibility and diagnostic precision of QFR during CAG in comparison to QCA with FFR as gold standard for physiological lesion evaluation.

1.2 Hypothesis

QFR has superior sensitivity and specificity for detection of functional significant lesions in comparison to QCA with FFR as gold standard

2. Materials and methods

2.1 Design

Prospective, observational, multicenter study with inclusion of 310 patients.

2.2 Patients

Consecutive patients referred for diagnostic angiography are screened for eligibility.

2.2.1 Inclusion criteria

- Stable angina pectoris or secondary evaluation of stenosis after acute MI
- Age > 18 years
- Able to provide signed informed consent

2.2.2 Angiographic inclusion criteria

- Indication for FFR in at least one stenosis:
 - o Diameter stenosis of 30%-90% by visual estimate
 - o Reference vessel size > 2 mm in stenotic segment by visual estimate

2.2.3 Exclusion criteria

- Myocardial infarction within 72 hours
- Severe asthma or severe chronic obstructive pulmonary disease
- Severe heart failure (NYHA \geq III)
- S-creatinine $>150\mu\text{mol}/\text{L}$ or GFR $<45\text{ ml/kg/1.73m}^2$
- Allergy to contrast media or adenosine
- Atrial fibrillation

2.2.4 Angiographic exclusion criteria

Lesion specific

- Below 30% and above 90% diameter stenosis by visual estimate.
- Reference size of vessel below 2 mm by visual estimation.
- Ostial LMCA lesions
- Ostial RCA lesions
- Distal LMCA lesions in combination with proximal Cx lesions
- Other bifurcation stenosis with lesions on both sides of a major shift ($>1\text{mm}$) in reference diameter

Angiographic quality

- Poor image quality precluding contour detection
- Good contrast filling not possible
- Severe overlap of stenosed segments
- Severe tortuosity of target vessel

2.3 Endpoints

2.3.1.1 Primary endpoint

Sensitivity and specificity of QFR in comparison to QCA with FFR as gold standard

2.3.1.2 Secondary endpoints

A) Feasibility of TIMI-flow based QFR in FFR assessed lesions

B) Diagnostic performance of TIMI-flow based QFR in comparison to FFR reported as

- 1) Sensitivity
- 2) Specificity

- 3) Positive predictive value
- 4) Negative predictive value
- 5) Positive and negative Likelihood ratio

C) Diagnostic grey zone. QFR limits for achieving 95% sensitivity and specificity in comparison to FFR

D) Diagnostic accuracy of TIMI-flow based QFR in comparison to 2D QCA (>50% diameter stenosis) as area under the curve

E) Diagnostic accuracy of three different methods for computing QFR

- 1) Fixed hyperemic flow rate (online computed)
- 2) TIMI flow based without hyperaemia (online computed)
- 3) TIMI flow based with hyperaemia (core laboratory computed)

F) Reproducibility of QFR

- 1) Fixed hyperemic flow rate (online computed vs core laboratory computed)
- 2) TIMI flow based without hyperaemia (online computed vs core laboratory computed)

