2.4.4 Detailed description of QFR computation

The Medis Suite QAngio XA-3D/QFR solution (Medis medical imaging system bv, Leiden, The Netherlands) is used for computation of QFR. The Medis Suite QAngio XA-3D/QFR solution is installed on a windows based computer. The analysis is performed as described in the manual provided with the software and in a step-by-step study specific standard operating procedure (Appendix A)

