2.4.5.2 Endpoint definitions: 3D Quantitative Coronary Angiography (3D-QCA)

- Percentual diameter stenosis: (Reference diameter \div minimal luminal diameter)/reference diameter in percent

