2.4.8 QFR core lab

The angiograms are reanalyzed by two observers blinded to any procedural results and FFR results. Analysis is performed using the three flow models; fixed hyperemic flow rate (HFR), TIMI flow based without hyperaemia and TIMI flow based with hyperaemia. Analysis is performed applying same principles as during on-line computation. Analysis is performed at the core laboratory for interventional imaging at Aarhus University Hospital, Denmark

3. Statistics and sample size

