3.1 Statistics

Baseline characteristics and procedural characteristics are presented as count and percentages, or if continuous variables are analyzed by mean and standard deviation if Gaussian distributed, else reported as medians and inter-quartile range. If more than one vessel is assessed per patient it is analysed on a per vessel level. Feasibility is calculated as the number of successful QFR/number of standard FFR times 100. The primary endpoint is calculated as superiority for sensitivity and specificity of QFR in comparison to QCA. The QCA value in analysis is the lesion site 3D QCA value obtained on-line during QFR analysis. Secondary endpoints include positive predictive value, negative predictive value, together with their 95% confidence intervals (CIs). The area under the curve by receiver-operating characteristic analysis is used to assess the diagnostic accuracy of QFR and QCA with FFR as gold standard. The diagnostic performance of QFR compared to 2D QCA is performed by one-tailed paired comparison of ROC curves (Hanley test). Pearson correlation is used to quantify the correlation between QFR and FFR. Agreement between QFR and FFR is assessed by Bland-Altman plot. Intra- and inter-patient variation in paired QFR and FFR values are compared to detect clustering. Analysis is performed using STATA 13.

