5.1 Data obtained in the study

Patient data recorded in the study database includes:

Site data entered in eCRF, data entered in the study CRF (CPR no. (only Denmark), patient identifier, hypertension, diabetes, prior PCI or CABG, indication for CAG, creatinine, GFR rate, hemoglobin, blood pressure, pulse, symptoms during adenosine infusion, adenosine infusion rate, FFR-result, time to QFR, time to FFR, QFR result (fixed and TIMI-flow based), clinical decision, treatment.

Site data transferred for documentation and analysis

1. Angiographic runs and documentation for the FFR wire position to be transferred in DICOM format (anonymized but marked with patient id, date, site, study name)
2. FFR traces:

Volcano systems

All raw study files are archived on DVD's (not USB memory sticks).

- 1) Locate the patient in the Volcano database.
- 2) Select the Archive button and then choose storage location (DVD).
- 3) Mark "Archive the study anonymously"

All cases should contain a dir. and SDY. file. Further, all screenshots that may have been acquired should be included.

St. Jude QUANTIEN systems

Find the patient in archive and select the export function.

- 1) Mark "to USB memory", "Internal", "Spreadsheet" and "Bitmap".
- 2) Select "Export all recordings in study"
- 3) Click the green export arrow

A typical filename for the raw data file (.DAT) may be:

{7DDB22A7-DEB9-49FA-B420-3AAE68CD870A}.dat

Do not rename the files.

St. Jude OPTIS (ILUMIEN/Integrated) systems

Find the patient and select the specific FFR traces. Click “export”.

- 1) Select native “RAW”
- 2) Select “anonymize” and “alternate patient ID” to type the patient-identifier
- 3) Identify export destination (USB/CD/DVD) and click export.

If there prior to export are cases stored on the selected storage device, the QUANTIEN and OPTIS systems asks if the selected case may be added to the existing database.

Transfer all the files from the CD or USB sticks to a separate folder on a hard drive, ZIP it (not by a Mac) and upload it to our trial system (TrialPartner).

3. Screen shot of final screen after each QFR computation

Missing data is verified as missing and indicated by unique coding.

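### Secondary endpoint D names a 2D QCA comparator for which no reading is described, and attaches a 50% cut-off to an area under the curve

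*Combined protocol and SAP*

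**What the plan says.** Section 2.3.1.2, endpoint D, sets the comparison: "Diagnostic accuracy of TIMI-flow based QFR in comparison to 2D QCA (>50% diameter stenosis) as area under the curve".

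Section 3.1 contains two statements about QCA. Directly after the sentence on the primary endpoint it says: "The QCA value in analysis is the lesion site 3D QCA value obtained on-line during QFR analysis". Further on, for the ROC analysis, it says: "The diagnostic performance of QFR compared to 2D QCA is performed by one-tailed paired comparison of ROC curves (Hanley test".

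The only QCA definition is in section 2.4.5.2, under the title "Endpoint definitions: 3D Quantitative Coronary Angiography (3D-QCA". Section 2.4.8 gives the core laboratory's angiographic work as follows: "Analysis is performed using the three flow models; fixed hyperemic flow rate (HFR), TIMI flow based without hyperaemia and TIMI flow based with hyperaemia". No 2D QCA reading appears there.

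Two other places bear on what could be measured. Section 5.1 lists, among the material sent by the sites, "Angiographic runs and documentation for the FFR wire position to be transferred in DICOM format". Section 2.4.4 refers for the analysis procedure to the software manual and to a "step-by-step study specific standard operating procedure (Appendix A". Neither of these was among the documents available for review.

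**The concern.** Endpoint D is the plan's AUC comparison of QFR with QCA, and it has its own named test. Two things about it are open.

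- **Which measurement.** An analyst who takes the QCA sentence in 3.1 as general would put a 3D value into an endpoint labelled 2D. An analyst who follows the label would need a 2D reading for which the supplied text gives no reader, software, blinding or choice of view. The choice of view matters because section 2.4.2 asks for two projections per vessel, so one lesion can yield more than one 2D percent stenosis.
- **Which coding.** An AUC summarises a marker over all thresholds, whereas endpoint D ties QCA to a single threshold. If QCA enters as yes/no while QFR enters as a continuous value, the QCA curve has one interior point. Its area is then lowered by the coding and not by the measurement.

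Two competent analysts could therefore report different AUC differences for the same endpoint, and a reader could not tell which one had been prespecified.

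**Working it through.** **Inputs.** All are from section 3.2: QCA at 50% diameter stenosis has sensitivity 0.48 and specificity 0.75; QFR has 0.74 and 0.91; 30% of the population is FFR-positive; power is 0.90 and alpha 0.05. Section 3.2 does not say whether the QCA figures are 2D or 3D. The plan states no AUC and no sample size for endpoint D.

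**Step 1: reproduce the plan's own figure, to fix the numbers of positives and negatives.** Connor's formula for McNemar's test, sensitivity comparison, with correlation −0.1:

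- Both tests positive: 0.48 × 0.74 − 0.1 × √(0.48 × 0.52 × 0.74 × 0.26) = 0.3333.
- Discordance ψ = (0.48 − 0.3333) + (0.74 − 0.3333) = 0.553; difference d = 0.26.
- n = [1.96√ψ + 1.2816√(ψ − d²)]² / d² = 81.8, rounded up to 82 FFR-positives.
- 82 / 0.30 = 273.3, rounded up to 274, which is the stated figure (two-sided).

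This gives 82 positives and 274 − 82 = 192 negatives.

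**Step 2: QCA as yes/no at 50%.** With a single cut-off, AUC = (sensitivity + specificity)/2 = (0.48 + 0.75)/2 = 0.615.

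**Step 3: QCA as a continuous marker through the same point.** Assume a binormal curve with slope b. Then a = z(sens) + b·z(spec) and AUC = Φ(a/√(1 + b²)).

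- b = 1: a = −0.050 + 0.674 = 0.624; AUC = Φ(0.624/√2) = 0.671.
- b = 0.7: AUC = 0.635.
- b = 1.4: AUC = 0.698.

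The loss from dichotomising is 0.671 − 0.615 = 0.056, with a range from 0.635 − 0.615 = 0.020 to 0.698 − 0.615 = 0.083.

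**Step 4: QFR as a continuous marker.** With b = 1, a = 0.643 + 1.341 = 1.984; AUC = Φ(1.984/√2) = 0.920.

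**Step 5: the gap.**

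| Coding of QCA | QCA AUC | QFR AUC | Difference |
|---|---|---|---|
| Continuous | 0.671 | 0.920 | 0.249 |
| Yes/no at 50% | 0.615 | 0.920 | 0.305 |

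**Step 6: would the test change?** Hanley–McNeil standard error: SE² = [A(1 − A) + (n₁ − 1)(Q₁ − A²) + (n₀ − 1)(Q₂ − A²)]/(n₁n₀), with Q₁ = A/(2 − A), Q₂ = 2A²/(1 + A), n₁ = 82 and n₀ = 192. The correlation between the two AUCs is not given; 0 to 0.5 is assumed.

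- Both continuous: SE of the difference 0.0428 to 0.0322; z = 5.8 to 7.7.
- QCA dichotomised: SE 0.0437 to 0.0330; z = 7.0 to 9.2. The formula is only approximate for a binary marker.

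Both are far beyond any conventional critical value.

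**The case against.** A reader might infer that endpoint D cannot be derived at all. The documents do not support that. The angiographic runs are collected in DICOM format, so a 2D percent stenosis can be read later, and Appendix A and the manual may describe more than the supplied text does. The absence of 2D QCA from the data list in section 5.1 proves nothing either, because that list names no 3D QCA item although 3.1 says the 3D value is obtained.

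A reader might also infer that the 50% cut-off does handicap QCA. No section says that QCA is dichotomised while QFR stays continuous. Section 3.1 speaks of ROC analysis for both QFR and QCA and plans a paired comparison of curves, which points to percent stenosis as a graded marker. The 50% may be no more than a label for the conventional test, as DS50 is in section 3.2.

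Finally, the two QCA statements in 3.1 need not conflict. The 3D sentence follows the primary endpoint and can be read as covering only that, with 2D reserved for endpoint D. A secondary endpoint may use a different comparator from the primary, and replacing a comparator that the plan names twice would change the question asked.

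These arguments reduce the point to one of specification, but they do not remove it. The restriction of the 3D sentence to the primary endpoint is an interpretation. No supplied text says how 2D QCA is read. The cut-off stands in the endpoint definition itself, where it can be applied literally.

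**Conclusion.** The point holds as a specification gap in one secondary endpoint. The dimension of QCA in endpoint D is stated inconsistently or, on the kinder reading, left without a described measurement. Its coding in the AUC is ambiguous.

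The numerical consequence is conditional. Literal use of the cut-off on QCA alone lowers its AUC by about 0.056 (0.020 to 0.083), and widens the QFR advantage from about 0.25 to about 0.30. With continuous percent stenosis the effect is zero. These figures rest on the planning sensitivities and specificities in section 3.2, a binormal model with slope 0.7 to 1.4 for QCA (equal variance for the central values and for QFR), and 274 independent observations.

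What is at risk is the size of the reported advantage and the identity of the comparator. Under the planning assumptions the test result would probably be the same. The primary endpoint is not affected, because 3.1 assigns it the 3D value.

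**What to change.** 1. In endpoint D of section 2.3.1.2, delete the parenthesis with the 50% cut-off. In endpoint D and in the ROC sentence of 3.1, state that QFR and QCA percent diameter stenosis both enter the ROC analysis as continuous variables. Keep the 50% cut-off for sensitivity and specificity only.
2. Reconcile the 2D and 3D statements. The sponsor can choose either route:
   - Use the 3D value already obtained on-line, so that endpoint D has the same comparator as the primary endpoint.
   - Keep 2D and limit the 3D sentence in 3.1 to the primary endpoint. Add to 2.4.8 a 2D QCA reading from the stored DICOM runs by the existing core-laboratory observers, who are already blinded to procedural and FFR results. Name the software and fix in advance which projection counts.

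The first route is a change of wording and needs no new data. The second costs one additional core-laboratory reading per lesion. In either case the reported AUC advantage of QFR may be slightly smaller than with a dichotomised QCA.

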2.4.2 Study procedure flow

The CAG procedure with FFR assessment is performed as normal best practice. QFR is calculated for all the vessels in which FFR assessment is planned. Angiographic projections are acquired

ensuring minimal overlap of the investigated vessels. Two projections of each vessel to be assessed are obtained at least 25 degrees apart. After initial diagnostic angiography the images are transferred to a workstation for calculation of the QFR-value. Not awaiting the result hereof, the operator continues the procedure by measuring standard FFR during I.V. hyperaemia. The FFR trace is recorded from before inducing hyperaemia to verification of drift not exceeding prespecified limits (section 2.4.3). The procedure is finalized as by normal practice according to the results of angiography and standard FFR. The QFR value is calculated in parallel and the results noted before knowing the measured FFR values. The QFR value may not be used for diagnosing the patient.

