2.4.2.1 Coronary angiography, detailed

Two good projections at least 25 degrees apart are required for the 3D vessel reconstruction.

Angiographic procedure:

- Inject I.C. nitro-glycerine as early as possible
- Use framerate of at least 12.5/15 frames/sec
- Make sure that the catheter is filled with contrast before the injection (i.e. after administration of nitro-glycerine)
- Use brisk, continuous and fast contrast injections. Aim for full 3 cardiac cycles

- Minimize overlap of target segments
- Avoid foreshortening of the vessel
- Avoid zooming
- Avoid moving the table early after injection
- Aim projections perpendicular to the target vessel
- Make sure that the entire vessel is visible in both projections. Both the proximal end and the potential position of the FFR pressure transducer should be visible in the same frame.

Suggested projections are found in table 1.

Vessel /Bifurcation	1st View	2nd View
LM + LAD/LCX	RAO 20, Caudal 45	AP, Caudal 10
LAD/Diag	AP, Cranial 45	RAO 35, Cranial 20
LCX/OM	LAO 10, Caudal 25	RAO 25, Caudal 25
Proximal+Mid RCA	LAO 45, CAUD 0	AP, CAUD 0
PLA/PDA	LAO 45, CAUD 0	LAO 30, CAUD 30

If only one good projection is identified, consider to use the *Acquisition Guide* tool in the Medis Suite QAngio XA 3D/QFR solution to identify the second projection:

1. Transfer first good projection to QFR computer (see section 2.4.2.2).
2. Right-click on the good projection and start QAngio3D.
3. Choose *Acquisition Guide* (**Figure 1**, red box). The yellow line on the angiography indicates the new projection angle, and should be approximately perpendicular to the target vessel at the lesion site.
 - a. If several lesions are located on the same vessel, a compromise must be made to ensure that most and the most severe lesions can be seen in the same projection.
4. Move the projection line by moving the yellow spot (**Figure 1**, arrow) in the Acquisition Guide indicator. Aim to keep the yellow spot inside the green area.
5. Position the C-arm as proposed by the guide.
6. In case of excessive overlap of the target segments and other vessels, rotate the C-arm 5 degrees around the axis of the target vessel.

a. If needed, use the Acquisition guide indicator again by maintaining the angulation of the yellow line and move the yellow spot just outside the green area – away from the red area. Move the C-arm accordingly.

[figure not shown]

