2.4.2.3 Angiographic run selection

Optimal projections are chosen according to the following criteria:

- Minimal overlap of the target vessel
- Good contrast injection, filling the entire vessel
- Includes both most proximal stenosis and most distal potential location of the pressure transducer of the subsequent FFR assessment

2.4.3 Detailed description of FFR recording:

The pressure wire is prepared and calibrated according to instructions for use. The pressure wire is advanced in the engaged guiding catheter and the pressure transducer positioned just outside the

tip of the catheter and equalized. After equalization, the wire is advanced to a position with the transducer in a stable position distal to the stenosis. In case of long healthy segments distal to the lesion, do not advance the FFR wire to a very distal position as this increases the complexity of acquiring appropriate angiographic views.

I.V. FFR recording: Recording of FFR during I.V. adenosine induced hyperemia is performed by femoral or brachial vein infusion of adenosine at $140 \mu\text{g L}^{-1}\text{min}^{-1}$. The infusion rate is increased to $200 \mu\text{g L}^{-1}\text{min}^{-1}$ if a stable FFR value is not achieved. At least 20 seconds of the lowest stable value is documented before obtaining an angiographic projection during hyperemia, which should at least be 25 frames/sec.

The entire FFR interrogation is recorded from before equalization and until a potential drift has been checked after retracting the pressure wire.

FFR is calculated as the ratio of distal mean pressure (Pd) measured by the pressure-wire to the proximal mean pressure (Pa) during hyperemia. The FFR cut-off for identification of a flow limiting stenosis is ≤ 0.80 for all lesions. The wire location is documented angiographically for all measurements. A pressure-wire pullback is performed to check for pressure-drift. A drift-value from 0.96-1.04 is accepted; otherwise, the procedure is repeated. For FFR values of 0.76-0.84, a drift with a narrower range of 0.98-1.02 is accepted.

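### Secondary endpoint E takes hyperaemic QFR from the core laboratory and the other two QFR methods from on-line site readings, so any contrast with the hyperaemic method mixes flow model with reader

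*Combined protocol and SAP*

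**What the plan says.** Endpoint E in section 2.3.1.2 covers the accuracy of three ways of computing QFR and gives a reading source for each. Method 1 (fixed flow) is an on-line value. Method 2 is "TIMI flow based without hyperaemia (online computed", also on-line. Method 3 is "TIMI flow based with hyperaemia (core laboratory computed".

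The two sources differ in people and setting:

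- **On-line.** Site staff trained by the software manufacturer do the computation (section 7.2) while the procedure is running. Section 2.4.2 states: "The QFR value is calculated in parallel and the results noted before knowing the measured FFR values".
- **Core laboratory.** Two observers, blinded to procedural and FFR results, reanalyse the angiograms (section 2.4.8). This covers every model: "Analysis is performed using the three flow models; fixed hyperemic flow rate (HFR), TIMI flow based without hyperaemia and TIMI flow based with hyperaemia". The same section adds: "Analysis is performed applying same principles as during on-line computation".

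Endpoint F uses the core-laboratory values of methods 1 and 2, but only for reproducibility against the on-line values. Section 3.1 uses the ROC area for diagnostic accuracy and names a paired ROC test only for QFR against 2D QCA. It gives no contrast between the three QFR methods.

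**The concern.** Listing three methods under one accuracy heading invites the reader to rank them. The background section describes the earlier QFR study as showing good accuracy "when QFR was based on angiographic views acquired with and without induced hyperaemia", so a natural use of E is to ask whether hyperaemia changes accuracy. Within E, however, no method-3 value has a comparator from the same reader.

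If method 3 looks better, the cause could be the flow model, or it could be that core-laboratory observers work off-line under different conditions from site staff. A real difference between flow models could equally be hidden by a reader effect of opposite sign. The plan does not say how the three results are to be set against each other, so nothing in it warns of this.

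**Working it through.** The plan gives no figure to reproduce for this point. The check is a comparison of the text, followed by an illustration on assumed values.

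**1. What is confounded**

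| Method in E | Source in E | Core-laboratory reading planned (2.4.8)? | Core-laboratory value used elsewhere? |
|---|---|---|---|
| 1 Fixed flow | On-line, site | Yes | F, reproducibility only |
| 2 TIMI flow, no hyperaemia | On-line, site | Yes | F, reproducibility only |
| 3 TIMI flow, hyperaemia | Core laboratory | Yes | Not in F |

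The contrast of 1 with 2 has a common source and is not affected. The contrasts of 3 with 1 and of 3 with 2 change flow model and reader together.

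**2. Is there a design reason?** For method 3, yes. Section 2.4.3 has the lowest stable FFR value "documented before obtaining an angiographic projection during hyperemia, which should at least be 25 frames/sec", whereas the on-line QFR has to be noted before FFR is known. An off-line reading of method 3 follows from that. It does not explain why the core-laboratory values of methods 1 and 2 are left out of E, since those values will exist.

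**3. How large could a spurious gap be?** Inputs:

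- 30% FFR-positive (section 3.2) and FFR cut-off 0.80 (section 2.4.3).
- Assumed, not in the documents: FFR normal with SD 0.07 or 0.09, QFR cut-off 0.80, and total reading-error SD s between 0.06 and 0.08.

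Model: FFR ~ N(0.80 + 0.524 × SD, SD), where 0.524 is the 70th percentile of the standard normal and gives 30% at or below 0.80. QFR = FFR + N(0, s). The flow model is the same for both readers and only s differs. ROC areas from 400,000 simulated vessels:

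| s | ROC area, FFR SD 0.07 | ROC area, FFR SD 0.09 |
|---|---|---|
| 0.06 | 0.868 | 0.907 |
| 0.07 | 0.841 | 0.884 |
| 0.08 | 0.816 | 0.862 |

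Gap = area (core laboratory) − area (on-line), with core-laboratory s = 0.06:

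- On-line s = 0.06: gap 0.
- On-line s = 0.07, an added error SD of √(0.07² − 0.06²) = 0.036: 0.868 − 0.841 = 0.027 and 0.907 − 0.884 = 0.023.
- On-line s = 0.08, an added error SD of √(0.08² − 0.06²) = 0.053: 0.868 − 0.816 = 0.052 and 0.907 − 0.862 = 0.045.

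The proportion correctly classified falls by about 2 points in the second case and 4 to 5 points in the third. If the core laboratory is the noisier reader, the inputs swap and the sign reverses: −0.023 to −0.027 for 0.07 against 0.06, and −0.045 to −0.052 for 0.08 against 0.06.

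**4. A second set of assumptions.** With FFR mean 0.86 and SD 0.10, model error SD 0.06 and core-laboratory reading error SD 0.03, one identical flow model has ROC area 0.908 at the core laboratory. From site readers with reading-error SD 0.03, 0.04 and 0.06 it has 0.908, 0.898 and 0.872, so the gaps are 0, 0.010 and 0.036.

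**The case against.** The strongest reply is that E plans no contrast. Where this protocol wants a comparison it says so, as in D and F. Three accuracy estimates against FFR, each with its source declared, are valid as they stand. The study's purpose is QFR during angiography (section 1.1), so on-line values are the natural target for methods 1 and 2. Neither the purpose nor the hypothesis asks about hyperaemia. The shared analysis principles, at least 20 supervised cases per site (section 7.2) and case-by-case feedback (section 7.3) should narrow any reader gap, and endpoint F would reveal a large one.

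Much of this is right. Each estimate is interpretable alone, on-line results should be kept, and how readers will use E is a judgement. But these measures do not show that the gap is zero. F measures agreement between two readings and does not give core-laboratory accuracy against FFR for methods 1 and 2. The lack of a stated contrast leaves the side-by-side listing unguarded.

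Two further objections stand as limits:

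- **The size is illustrative.** The error SDs are assumed, and the model is not calibrated to the plan's own figures. Sensitivity 0.74 and specificity 0.91 at 30% positive give 0.30 × 0.74 + 0.70 × 0.91 = 0.859 correctly classified, against 0.795 to 0.833 in the illustration at s = 0.06.
- **A common reader does not isolate the flow model.** Method 3 uses a separate hyperaemic run with a 25 frames/sec minimum, while the standard angiogram instruction is "Use framerate of at least 12.5/15 frames/sec".

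**Conclusion.** The concern holds. As E is defined, any accuracy difference between method 3 and methods 1 or 2 cannot be attributed to the flow model, because the reader and setting change with it. The documents fix neither the size nor the direction of the effect. Under the assumed reading-error SDs of 0.06 to 0.08, the spurious gap in ROC area lies between 0 and about 0.05 in either direction. It depends wholly on those assumptions and is not an estimate for this study.

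The reach is limited. This is one secondary endpoint, the contrast of methods 1 and 2 is sound, and the primary endpoint and sample size are untouched. It is worth correcting because the like-for-like readings are already planned, and settling the reading source in advance avoids choosing it once results are known.

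**What to change.** Amend endpoint E and section 3.1 as follows:

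1. Compare the three QFR methods pairwise on core-laboratory readings, in vessels with all three values and a valid FFR. Report paired differences in ROC area with 95% confidence intervals.
2. Say how the two core-laboratory observers' readings are combined into one value per vessel.
3. Report the on-line accuracy of methods 1 and 2 beside this, labelled as in-procedure performance, and do not set it against method 3.
4. Report the number of vessels without a usable hyperaemic run.
5. State that a common reader removes the reader difference but not the acquisition difference, since method 3 rests on a separate run with a different minimum frame rate.

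The cost is wording in the analysis plan, with no new readings. The downside is that the comparison is restricted to vessels with a usable hyperaemic run, which may be a selected subset; item 4 shows how many are lost.
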